2.8.6 Other safety data

2.8.6.1 ECG and cardiac imaging data

The average of the replicates of the ECG parameters at each assessment should be used in the analyses.

12-lead ECGs including PR-interval, QRS, QT, QTcF, and hearth rate intervals will be obtained for each subject during the study. ECG data will be read and interpreted locally.

The number and percentage of subjects with notable ECG values will be presented.

- QT and QTcF
 - New value of > 450 ms and ≤ 480 ms
 - New value of > 480 ms and ≤ 500 ms
 - New value of > 500 ms
 - Increase from baseline of > 30 ms to ≤ 60 ms
 - Increase from baseline of > 60 ms
- Heart rate
 - Increase from baseline $>25\%$ and to a value > 100 bpm
 - Decrease from baseline $>25\%$ and to a value < 50 bpm
- PR-interval
 - Increase from baseline $>25\%$ and to a value > 200 ms
 - New value of > 200 ms
- QRS
 - Increase from baseline $>25\%$ and to a value > 120 ms
 - New values of QRS > 120 ms.

A listing of all ECG assessments will be produced by treatment arm and notable values will be flagged. In the listing, the assessments collected during the post-treatment period will be flagged.

2.8.6.2 Vital signs

Vital sign assessments are performed in order to characterize basic body function. The following parameters were collected: height (cm), weight (kg), body temperature ($^{\circ}\text{C}$), heart rate (beats per minute), systolic and diastolic blood pressure (mmHg).

Vital signs collected during on-treatment will be summarized. A listing of subjects with notable vital signs will be provided and values measured during the post-treatment follow up will be flagged in the listing. The number and percentage of subjects with notable vital sign values (high/low) will be presented by treatment arm.

Table 2-3 Criteria for notable vital sign values

Vital sign (unit)	Notable high value	Notable low value
Weight (kg)	increase $\geq 10\%$ from baseline	decrease $\geq 10\%$ from baseline
Systolic blood pressure (mmHg)	≥ 180 and increase from baseline of ≥ 20	≤ 90 and decrease from baseline of ≥ 20
Diastolic blood pressure (mmHg)	≥ 105 and increase from baseline of ≥ 15	≤ 50 and decrease from baseline of ≥ 15
Heart rate (bpm)	≥ 100 and increase from baseline of $> 25\%$	≤ 50 and decrease from baseline of $> 25\%$
Body temperature ($^{\circ}\text{C}$)	≥ 39.1	--

2.9 Pharmacokinetic analysis

All PK analyses will be performed for INC280 and pembrolizumab based on the PAS. PK parameters will be determined by non-compartmental method(s) using the PK profile of capmatinib. For Capmatinib, PK parameters will be derived and reported, when feasible include but may be not limited to those listed in [Table 2-4](#). For pembrolizumab, PK parameters to be reported will include but may not be limited to Ctrough.

Table 2-4 Non-compartmental pharmacokinetic parameters

PK parameter	Definition
AUClast	The AUC from time zero to the last measurable analyte (capmatinib or pembrolizumab) concentration sampling time (tlast) (mass × time × volume ⁻¹)
AUCtau	The AUC calculated to the end of a dosing interval (tau) at steady-state (amount × time × volume ⁻¹)
Cmax	The maximum (peak) observed plasma, blood, serum, or other body fluid drug concentration after single dose administration (mass × volume ⁻¹)
Ctrough	The minimum (peak) observed plasma serum concentration (mass x volume ⁻¹)
Tmax	The time to reach maximum (peak) plasma, blood, serum, or other body fluid drug concentration after single dose administration (time)
T1/2	The elimination half-life associated with the terminal slope (λz) of a semi logarithmic concentration-time curve (hr). Use qualifier for other half lives.
CL/F	The apparent total body clearance of drug from the plasma (L/hr)
Vz/F	The apparent volume of distribution during terminal phase (associated with λz) (L)

2.9.1 Data handling principles

All concentrations below the LLOQ or missing data will be labeled as such in the concentration data listings. Concentrations below the LLOQ will be treated as zero in summary statistics and for the calculation of PK parameters, unless otherwise stated under the PAS.

At the time of analysis, concentration data from subjects may be removed from the estimation of certain PK parameters depending on the number of available blood samples, concomitant medications, vomiting, etc. Specific time points might be removed from the analysis set if technical issues with the sample are reported (e.g., sampling issues, missing information). These subjects and concentration data points will be identified at the time of analysis.

2.9.2 Data analysis set

All PK data analyses and PK summary statistics will be based on the PAS (details in section 2.2). Only PK blood samples with date and time and for which the last prior dose dates and times are adequately recorded will be included in the PK analyses.

2.9.3 Basic tables, figures, and listing

Descriptive statistics will be presented for all PK parameters ([Table 2-5](#)), as described below.

Table 2-5 Descriptive analysis

Parameters	Descriptive statistics
------------	------------------------

AUC ⁽¹⁾ , C _{max} , C _{trough} , CL/F, T _{1/2} , Vz/F	Mean standard deviation, CV% mean, geometric mean, CV% geo-mean, median, minimum, and maximum.
T _{max}	Median, minimum, and maximum.

⁽¹⁾ Includes all AUC parameters

CV% = standard deviation/mean×100

CV% geo-mean = sqrt (exp (variance for log transformed data)-1)×100

Zero concentrations will not be included in the geometric mean calculations. Tmax will be summarized in terms of median values and ranges. Missing values for any PK parameters or concentrations will not be imputed and will be treated as missing.

A listing of derived PK parameters per subject will be produced by treatment arm.

Analysis of drug concentrations

Descriptive statistics for drug concentrations, including n, m (number of non-zero concentrations), arithmetic mean, CV% mean, SD, median, geometric mean, CV% geo-mean, minimum and maximum, will be presented at each scheduled time point by treatment. Zero concentrations will not be included in the geometric mean calculation.

The mean (+/- SD) and geometric mean concentration-time profiles of Capmatinib on C2D1 will be displayed graphically on the linear and semi-log view.

2.10 Immunogenicity and PK/Pharmacodynamics analyses

Another secondary objective is to evaluate the prevalence and incidence of immunogenicity.

2.10.1 Immunogenicity

2.10.1.1 Sample ADA status

Each IG sample is assessed in a three tiered ADA testing approach. All IG samples are analyzed in the initial screening assay (first tier). Only samples testing positive in the screening assay are then subjected to the confirmatory assay to demonstrate that ADA are specific for pembrolizumab (second tier). The titer of confirmatory positive samples will be subsequently determined in the titration assay (third tier). Samples can test negative in either the screening or confirmatory assay but for analysis purposes they will not be differentiated. The following properties of each sample will be provided in the source data:

- Result of assay according to pre-specified confirmatory cut point: ADA positive (yes) or ADA negative (no)
- Titer (for positive samples): numerical representation of the magnitude of ADA response
- Fold titer change (i.e., x-fold): threshold for determining treatment boosted.

Sample ADA status is determined based on the following definitions:

- Unevaluable sample: Sample where assay is not available.
- Determinant sample: Sample that is neither ADA-inconclusive nor unevaluable.

The following definitions apply only to determinant samples:

- ADA-negative sample: Determinant sample where assay is ADA negative and pembrolizumab PK concentration at the time of IG sample collection is less than the drug tolerance level.
- ADA-positive sample: Determinant sample where assay is ADA positive.

The following definitions apply only to post-baseline ADA-positive samples with a corresponding determinant baseline sample. To be classified as treatment-boosted or treatment-unaffected, both the post-baseline and baseline titer must be non-missing:

- Treatment-induced ADA-positive sample: ADA-positive sample post-baseline with ADA-negative sample at baseline.
- Treatment-boosted ADA-positive sample: ADA-positive sample post-baseline with titer that is at least the x fold titer change greater than the ADA-positive baseline titer.
- Treatment-unaffected ADA-positive sample: ADA-positive sample post-baseline with titer that is less than the x fold titer change greater than the ADA-positive baseline titer.

NOTE: The fold titer change is provided in the method validation report by Drug Metabolism & Pharmacokinetics (DMPK) and it is described in the bioanalytical data report.

The following summaries of sample ADA status (n and %) will be provided using IG prevalence set:

- ADA-positive samples (i.e., ADA prevalence) both overall and by time point (including baseline). For summaries by time point, the denominator is the number of subjects at that time point with a determinant sample.

Listings will be provided of sample ADA status (including titer for positive samples).

2.10.1.2 Subject ADA status

Any IG sample collected after more than 150 days of the last dose of pembrolizumab will not be used for summaries or derivations and will only be included in the listing.

[figure not shown]
Subject ADA status is defined as follows:

[figure not shown]
- Treatment-induced ADA-positive subject: subject with ADA-negative sample at baseline and at least one treatment-induced ADA-positive sample.
- Treatment-boosted ADA-positive subject: subject with ADA-positive sample at baseline and at least one treatment-boosted ADA-positive sample.
- Treatment-unaffected ADA-positive subject: subject with ADA-positive sample at baseline, no treatment-boosted ADA-positive samples, and at least one treatment-unaffected ADA-positive sample.
- Treatment-reduced ADA-positive subject: subject with ADA-positive sample at baseline and at least one post baseline determinant sample, all of which are ADA-negative samples.
- ADA-negative subject: subject with ADA-negative sample at baseline and at least one post baseline determinant sample, all of which are ADA-negative samples.
- Inconclusive subject: subject who does not qualify as treatment-induced ADA-positive, treatment-boosted ADA-positive, treatment-unaffected ADA-positive, treatment-reduced ADA-positive, or ADA-negative.

The following summaries of subject ADA status (n and %) will be provided using IG incidence set:

- Treatment-boosted ADA-positive subjects; denominator is the number of subjects with ADA-positive sample at baseline.
- Treatment-induced ADA-positive subjects; denominator is the number of subjects with ADA-negative sample at baseline.
- ADA-negative subjects: denominator is the number of subjects in IG incidence set.
- ADA-positive subjects (i.e., ADA incidence): calculated as the number of treatment-boosted ADA-positive and treatment-induced ADA-positive subjects; denominator is the number of subjects in IG incidence set.

Listings will be provided of subject ADA status.

Final

[REDACTED]

[REDACTED]

[REDACTED]

[REDACTED]

[REDACTED]

[REDACTED]

2.13 Interim analysis

An administrative efficacy interim analysis was planned to be conducted by an independent statistician and an independent programmer supporting the DMC, when approximately 30 PFS events have been observed. Results were planned to be reviewed by the DMC and then shared with a Novartis Committee (independent to the study team) in order to make development decisions for other or future studies. The aggregated safety data was planned to be monitored on a regular basis by the DMC (as defined in Section 10.2.1 of the protocol).

Following approval of protocol amendment 03, the planned administrative efficacy interim analysis will not be performed.

3 Sample size calculation

Sample size calculation was based on simulations for various scenarios on-treatment outcome, number of subjects included, number of events at the time-point of the primary analysis using the Bayesian model defined in protocol Section 16.3, which will no longer be performed.

The evaluation of the success criteria was based on the HR of the PFS (capmatinib plus pembrolizumab vs pembrolizumab alone) after the time-point of risk change in the assumed two-piece exponential distributions (HR2) used in the Bayesian model (in order to account for potential delayed effects).

The success criteria used for the evaluation of the efficacy of the simulation samples are the following:

- At least 50% confidence level that $HR2 \leq 0.7$
- At least 90% confidence level that $HR2 < 1$

Approximately 96 subjects will be enrolled in the study, randomized with ratio 2:1 (capmatinib plus pembrolizumab : pembrolizumab alone). In this calculation, a 6% rate of early drop-out before 1st post-baseline assessment as well as a 10% risk of drop-out rate per year on-treatment has been taken into consideration.

Regarding the enrolment plan of the study, we assume that 3 subjects will be accrued at the first month after first subject first visit, 6 at the second, 12 at the third, 14 at the fourth and 15 subjects per month for all the following months until approximately 96 subjects are enrolled.

The reported median PFS for pembrolizumab alone as first-line therapy for NSCLC subjects with $PD-L1 \geq 50\%$ was 10.3 months in KEYNOTE-024 study (Reck et al 2016) and 7.1 months

in KEYNOTE-042 (Mok et al 2019). It is therefore reasonable to assume that the median PFS of pembrolizumab is between 7.1 and 10.3 months. We expect around 50% reduction in the HR2 of PFS in capmatinib plus pembrolizumab, after the time-point of risk change in the assumed two-piece exponential distributions.

Table 3-1 presents the operating characteristics of the Bayesian model with different outcome scenarios keeping stable the total sample size (96 subjects) and the number of total PFS events (50) required at the time-point of the primary analysis. With this combination reasonable operating characteristics can be achieved. Description of operating characteristics of alternative sample size can be found in Section 16.3 of the protocol.

Table 3-1 Operating characteristics for scenarios with 96 subjects and 50 events at the primary analysis

Scenarios (capmatinib plus pembrolizumab vs. pembrolizumab) PFS in months (Hazard ratio)	Probability of Success
7.1 vs. 7.1 months (HR2=1)	0.110
8.5 vs. 8.5 months (HR2=1)	0.160
10.3 vs. 10.3 months (HR2=1)	0.196
12.8 vs. 8.5 months (HR2=0.598)	0.716
12 vs. 7.1 months (HR2=0.505)	0.850
15 vs. 8.5 months (HR2=0.496)	0.855
18.5 vs. 10.3 months (HR2=0.501)	0.840

HR2: Hazard ratio after the risk change in the two-piece exponential distributions

4 Change to protocol specified analyses

No change from protocol specified analysis was made.

5 Appendix

5.1 Imputation rules

5.1.1 Study drug

5.1.1.1 Data Imputation for the last administration

The following rule should be used for the imputation of date of last administration for a given study treatment component:

Scenario 1: If the date of last administration is completely missing and there is no EOT eCRF page, the subject is considered as on-going:

The subject should be considered as on-treatment. In this case, the cut-off date should be used as the last dosing date for exposure calculations.

Scenario 2: If the date of last administration is completely or partially missing and the EOT eCRF page is available (prior to any death date or withdrawal of consent date, if available):

Case 1: The date of last administration is completely missing, and the EOT visit date is complete, then this latter date should be used.

Case 2: Only Year(yyyy) of the dose end date is available and yyyy < the year of EOT date:

Use Dec31yyyy

Case 3: Only Year (yyyy) of the dose end date is available and yyyy = the year of EOT date:

Use EOT date

Case 4: Both Year (yyyy) and Month (mm) are available for the date of last administration, and yyyy = the year of EOT date and mm < the month of EOT visit:

Use last day of the Month (mm).

After imputation, compare the imputed date with the start date of that specific record, if the imputed date is < start date of that record

Use the start date of that record.

Subjects with missing start dates are to be considered missing for all study treatment component related calculations described in [Section 2.5.1](#) and no imputation will be made. If the date of first administration is missing, then the date of last administration should not be imputed.

5.1.1.2 Data Imputation of the first administration

Subjects with missing start dates are generally considered missing for all study treatment component related calculations described in [Section 2.5.1](#) and no imputation will be made. If the date of first administration is missing, then the date of last administration should not be imputed.

5.1.2 AE date imputation

A missing AE start date will be imputed using the logic matrix described in [Table 5-1](#).

Table 5-1 Imputation rules for a partially missing AE start date

	AEM missing	AEM<TRTM	AEM=TRTM	AEM>TRTM
AEY missing	Not imputation	Not imputation	Not imputation	Not imputation
AEY<TRTY	(D)	(C)	(C)	(C)
AEY=TRTY	(B)	(C)	(B)	(A)
AEY>TRTY	(E)	(A)	(A)	(A)

AEM=Month AE started, AEY=Year AE started

TRTM=Month treatment started, TRTY=Year treatment started

[Table 5-2](#) is the legend to the logic matrix shown in [Table 5-1](#) and details the relationship of AE start date to study treatment start date.

Table 5-2 Imputation legend and AE/treatment start date relationship

AE start date relationship	Imputation
(A) After treatment start or uncertain	MAX(01MMMYYYY, TRTSDT+1)
(B) Uncertain	TRTSDT+1

AE start date relationship	Imputation
(C) Before treatment start	15MMMYYYY
(D) Before treatment start	01JULYYYY
(E) After treatment start	01JANYYYY

Before treatment start: Partial date indicates AE start date is prior to treatment start date.
After treatment start: Partial date indicates AE start date is after treatment start date.
Uncertain: Partial date insufficient to determine relationship of AE start date to treatment start date.

No imputation will be performed for missing/incomplete AE end dates. AE with uncertain relationship will be considered as on-treatment AE.

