2.1.1.5 On-treatment assessment/event and observation periods

For all safety reporting the overall observation period will be divided into three mutually exclusive segments:

- **pre-treatment period:** from day of subject's informed consent to the day before first administration of study treatment
- **on-treatment period:** from date of first administration of study treatment to 30 days after date of last administration of study treatment (including start and stop dates)
- **post-treatment period:** starting at Day 31 after last administration of study treatment.

If dates are incomplete in a way that clear assignment to pre-, on-, post-treatment period cannot be made, then the respective data will be assigned to the on-treatment period.

Safety summaries (tables, figures) include only data from the on-treatment period with the exception of baseline data which will also be summarized where appropriate (e.g., change from baseline summaries). In addition, a separate summary for death including on-treatment and post-treatment deaths will be provided. In particular, summary tables for AEs will summarize only on-treatment events, with a start date during the on-treatment period (treatment-emergent AEs).

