2.4.3.3 Concomitant therapies

Concomitant therapies are defined as all interventions (therapeutic treatments and procedures) other than the study treatment administered to a subject coinciding with the study treatment period. Concomitant therapy include medications (other than study drugs) starting on or after the start date of study treatment or medications starting prior to the start date of study treatment and continuing after the start date of study treatment. Concomitant medications will be listed by subject and summarized by ATC class and treatment arm.

The summaries will include:

- Medications starting on or after the start of study treatment but no later than 30 days after last dose of study treatment and
- Medications starting prior to start of study treatment and continuing after the start of study treatment.

The imputation of a concomitant medication start date will follow the same conventions as for an AE start date. No imputation will be performed for concomitant medication end dates.

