5.1.3 Concomitant medication date imputation

The imputation of a concomitant medication start date will follow the same conventions as for an AE start date (see [Section 5.1.2](#)). No imputation will be performed for concomitant medication end dates.

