5.1.3.1 Prior therapies date imputation

Start date

The same rule which is applied to the imputation of AE/concomitant medication start date will be used with the exception that scenario (B) will be replaced to be 'start date of study treatment - 1' (see [Section 5.1.2](#)).

End date

Imputed date = min (start date of study treatment, last day of the month), if day is missing;

Imputed date = min (start date of study treatment, 31DEC), if month and day are missing.

If the end date is not missing and the imputed start date is after the end date, use the end date as the imputed start date.

If both the start date and the end date are imputed and if the imputed start date is after the imputed end date, use the imputed end date as the imputation for the start date.

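### SAP 5.1.2 and 5.1.3 can impute a partial start date to the day after first dose even when the known end date is before first dose, so the record counts as on-treatment

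*SAP*

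**What the plan says.** SAP 5.1.2: "A missing AE start date will be imputed using the logic matrix described in" Table 5-1. The matrix has two inputs, the start month and start year, each compared with those of treatment start. Cell (B) covers a start in the treatment year whose month is missing or is the treatment month. Table 5-2 labels it uncertain and sets the start to treatment start plus one day. The legend judges uncertainty from the partial start alone: "Uncertain: Partial date insufficient to determine relationship of AE start date to treatment start date". The section closes with two rules: "No imputation will be performed for missing/incomplete AE end dates", and "AE with uncertain relationship will be considered as on-treatment AE".

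SAP 5.1.3 carries this to medication: "The imputation of a concomitant medication start date will follow the same conventions as for an AE start date".

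Classification then depends on the start date. For AEs, SAP 2.1.1.5 says "summary tables for AEs will summarize only on-treatment events, with a start date during the on-treatment period (treatment-emergent AEs". For medication, the first summary category in SAP 2.4.3.3 is "Medications starting on or after the start of study treatment but no later than 30 days after last dose of study treatment", with no condition on the end date.

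SAP 5.1.3.1, on prior therapies, does look at the end date: "If the end date is not missing and the imputed start date is after the end date, use the end date" as the start.

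**The concern.** An AE or drug that ended before first dose cannot have begun after it, so its position relative to treatment is not in doubt. Cell (B) treats it as in doubt because it never reads the end date. The result is a record that starts after it ends, in the wrong period.

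This departs from two principles in the same SAP. Section 2.1.1.5 uses on-treatment as the default only for records whose dates do not allow them to be placed in a period. Section 2.4.3.3 defines concomitant therapy as therapy that overlaps study treatment.

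At stake is the accuracy of the treatment-emergent AE and concomitant-medication tables. Enrollment was halted for tolerability, so the AE tables carry much of what this trial will report. Efficacy and sample size are not touched.

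**Working it through.** The plan states no figure to reproduce. The check applies Tables 5-1 and 5-2 literally to records that ended before first dose.

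**Can such records arise?** Yes. Protocol 10.1.1 collects AEs from informed consent, Protocol Table 8-1 sets screening at Day -28 to Day -1, and Protocol Table 8-2 records prior and concomitant medication at screening.

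**Each cell, for a record that ended before first dose**

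| Cell | Partial start | Imputed start | Moved across first dose? |
|---|---|---|---|
| (A) | later month in the treatment year, or later year with month known | later of the 1st of that month and first dose + 1 | cannot arise |
| (B) | treatment year, month missing or equal to treatment month | first dose + 1 | **always** |
| (C) | earlier month in the treatment year, or earlier year with month known | 15th of that month | no |
| (D) | earlier year, month missing | 1 July of that year | no |
| (E) | later year, month missing | 1 January of that year | cannot arise |

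Cells (C) and (D) can also put the start after the end. For example, a May 2020 start with end 10 May becomes 15 May. The record still stays before first dose.

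**Examples, first dose 20 June 2020**

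- Start June 2020 (day missing), end 12 June 2020. Cell (B) gives 21 June, which is 21 − 12 = 9 days after the event ended; it is counted as on-treatment. With the cap, start = min(21 June, 12 June) = 12 June, pre-treatment.
- Start 2020 (day and month missing), end 5 June 2020. Cell (B) gives 21 June, 16 days after the end. With the cap, 5 June.
- Start 2020, end May 2020 (day missing). This plainly ended before first dose, but an incomplete end date is not imputed, so a cap that needs a complete end date has nothing to work on and the start stays at 21 June. The cap alone does not cover this case.

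**Share of partial-start records reached by cell (B).** This rests on an assumption: every first-dose date in 2020, and every start/end pair inside a look-back window before first dose, equally likely.

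| Window | Day missing | Day and month missing |
|---|---|---|
| 28 days (screening) | 56,028 / 148,596 = 38% | 140,882 / 148,596 = 95% |
| 180 days (assumed, for medication) | 56,760 / 5,962,140 = 1% | 4,001,910 / 5,962,140 = 67% |

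The denominators are 366 × (1 + … + 28) = 366 × 406 and 366 × (1 + … + 180) = 366 × 16,290. Every cell (B) record is misclassified; with the cap and complete end dates, none is. These are shares of records that already have a partial start and ended before first dose, not shares of all records.

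**Effect per affected subject.** Protocol Amendment 3 gives 51 and 25 subjects randomized. If the Safety set has the same sizes, one extra subject in a preferred term is 1/25 = 4.0 points or 1/51 = 2.0 points.

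**Does the cap remove anything it should keep?** No. A record leaves the on-treatment period only if its end date is before first dose, and its true start is then before first dose too. A record ending on or after first dose remains on-treatment.

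**The case against.** **Other sections may already settle it.** Section 2.1.1.5 defaults to on-treatment only when a record cannot be placed, and a known pre-dose end date places it. Section 2.4.3.3 requires overlap with treatment. Both show what the SAP intends. Neither overrides an explicit instruction to set the start to first dose plus one, and the tables select on start date. The sections need reconciling.

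**The cap may already apply.** Section 5.1.3.1 sits under 5.1.3, and its heading does not restrict it to anti-neoplastic therapy. But it covers prior therapies, is called from 2.4.3.1, and replaces the cell (B) value with the day before treatment start. It is therefore a different rule from the one 5.1.3 gives for concomitant medication, and it does not reach AEs.

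**The programming specifications may contain the check.** SAP section 1 places derived-variable specifications in a separate document that is not available here. This stands as a limit: the SAP rule is wrong as written, but one cannot say that the final tables will be.

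**Counting doubtful events as on-treatment is conservative.** That is a fair convention where doubt exists. Here there is none.

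**A stronger reading to avoid.** A reader might infer that events and drugs ending before first dose are generally counted as treatment-emergent or concomitant, or that the comparison of AE rates between arms is biased. The documents support neither. Three conditions must hold together: a partial start, cell (B), and an end before first dose. Conditions present at consent go to medical history (Protocol 10.1.1) and missing values are queried (Protocol 11.2), so such AE records should be uncommon. Protocol 6.1.1 puts Cycle 1 Day 1 within 3 days of randomization, so most of these events precede randomization. There is no reason to expect them to differ systematically by arm; a chance difference of a subject or so in a term remains possible. Nor do the documents show that medication is affected more often than AEs: the table above gives 67% or 1% depending on which part of the date is missing.

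**Conclusion.** The point holds for cell (B) of Tables 5-1 and 5-2 and for the same cell as applied to concomitant medication by 5.1.3. A record with such a partial start and an end known to precede first dose is given a start after its own end and assigned to the wrong period.

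The effect is minor. The number of records is not given and is probably small. Each affected subject adds at most one to the count for a term, 4.0 or 2.0 points on the assumption that the Safety set arms have 25 and 51 subjects. Those are randomized counts; the Safety set sizes are not stated. Because SAP 2.8.1 counts a subject once per category, a subject with a genuine on-treatment event of the same term adds nothing. The error is always towards over-counting.

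**What to change.** Make two additions to SAP 5.1.2, and state that they also apply under 5.1.3:

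1. The cap already used in 5.1.3.1: when the end date is available and the imputed start is later than it, take the end date as the imputed start.
2. A classification rule: when the end date, complete or partial, already shows that the record ended before first dose, class an AE as pre-treatment and a medication as prior. A partial end date shows this when the latest day consistent with it is before first dose. If it could still fall on or after first dose, the present on-treatment default stays.

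The second sentence is needed because the first does not act on an incomplete end date. The cap also removes start-after-end dates in cells (C) and (D), with no change of period there.

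The cost is two sentences in a SAP amendment and a short change to the date derivation. No new data are needed.
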